### **6.0 Procedures Involved**

#### **6.1 Study Design**

This is a double-blind, randomized controlled trial (RCT) with two treatment arms:

Arm 1 - Omega-3 (EPA+DHA) – Dose is 2,100mg per day via 3 mini-capsules, 2x/day (a total of 6 mini-capsules per day). Each capsule has 252mg of EPA and 102mg of DHA.

Support for dosing:

- The American Heart Association (AHA) says taking up to 3 grams of fish oil daily in supplement form is considered safe [33]
- Up to 5,000mg of omega-3 fatty acids per day is considered safe [34].
- The U.S. Food and Drug Administration recommends consuming no more than 3 g/day of EPA and DHA combined, including up to 2 g/day from dietary supplements.[35]

Arm 2 - Placebo – made from soybean oil (same dosing schedule as intervention arm)

Supplement and placebo will be supplied by KD Pharma.

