## 9.0 Study Timelines

Each subject will spend 12 weeks in the study.

It is anticipated that all subjects will be enrolled within a 6-month timeframe.

	Month 1	Month 2	Month 3	Month 4	Month 5	Month 6	Month 7	Month 8	Month 9	Month 10	Month 11	Month 12
IRB approvals & startup	X	X	X									
Enrollment				X	X	X	X	X				
Subjects on study (12 weeks)				X	X	X	X	X	X	X	X	X
Interim analysis at 3 weeks					X							
Final data analysis										X	X	X

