#### **14.0 Withdrawal of Subjects**

If a subject needs to be withdrawn from the study without their consent for medical reasons or non-compliance, she or he will be notified by [name] or [name] by phone, with a follow-up letter mailed to the subject's home.

If a subject chooses to withdraw from the study, she or he must notify the PI by calling the phone number on the consent form. All data collected up to the point of termination will be kept in the study.

Any subject missing both daily doses 3 times a week for 3 weeks in a row will be removed from the study for non-compliance, and asked to dispose of any unused study supplement/placebo.

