## Follow-up Survey - Covid Recovery Study

Please complete the survey below.

Thank you!

Were the instructions on how to take the pills clear?

Yes  
 No  
 Neutral / I don't know

If no, why not?

Did you not take the pills (skip one or more doses) at any time during 12-week study? (please refer to your pill log calendar)

No  
 Yes

If yes, how often did you not take the pills?

For how many days in a typical week did you take the pills?

Please include any comments about missed doses here:

Were the pills easy to take?

Yes  
 No  
 Neutral / I don't know

If no, why not?

Did taking the pills interfere with your daily activities somehow?

Yes  
 No  
 Neutral / I don't know

If yes, how?

How satisfied were you with your experience taking the pills?

Very satisfied  
 Satisfied  
 Neutral  
 Dissatisfied  
 Very dissatisfied

Are you willing to be contacted in the future about opportunities to participate in other research studies?

Yes  
 No

Confidential

Page 2

Since starting your participation in this study, has any doctor or other health care provider told you that you have any of the following illnesses? (please check all that apply)

- Diabetes or high blood sugar
- Hypertension or high blood pressure
- High cholesterol
- Stroke (ischemic or hemorrhage)
- Chronic lung disease such as asthma, emphysema, or chronic bronchitis
- Heart disease
- Cancer (other than skin cancer)
- Depression
- HIV/AIDS
- Other

If you answered "Other," please specify:

---

Please share anything else you would like us to know about your experience participating in this study:

---

During the 12-week study, did you receive the covid-19 vaccine?

Yes  
 No

If you did receive the covid-19 vaccine, did you experience any side effect(s)?

---

For how long did you experience side effect(s)? (please specify in # of days)

---

Is there anything else you would like to tell us that you might be important that we did not ask about?

---

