## Study Discontinuation Verification

Please complete the survey.

Thank you!

- 1) Have you discontinued study participation?  Yes  No
- 2) How many pills altogether do you have in your bottle(s) of supplement/placebo? \_\_\_\_\_
- 3) Please discard all of the study supplement/placebo pills that you have, and indicate that here. Have you discarded your study supplement/placebo?  Yes  No

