 **Product Details**

 **Supplement Facts**

 **Reviews**

**OMEGA-3 MINICAPS** deliver 700 mg of our high-purity pure omega-3 fatty acids in two easy-to-swallow mini-softgels. **OMEGA-3 MINICAPS** are the perfect way complement your wellness program and ensure you and your family are getting enough omega-3 fatty acids in your diet. **OMEGA-3 MINICAPS** are the highest concentration omega-3 fish oil available in pharmacies. They come in a great-tasting vanilla flavor. Each **MINICAP** contains 350 mg of omega-3's, which is three and a half times as strong as standard krill oil products.

**Supports Heart Health and Blood Circulation:** Supportive but not conclusive research shows that consumption of EPA and DHA omega-3 fatty acids with healthy diet and exercise may reduce the risk of coronary heart disease.

**A "Clean" Natural Source:** All our omega-3s come from wild-caught anchovies and sardines with zero to low mercury exposure off the coast of Peru.

**No Fishy-ness:** The purity of our oil - plus a natural orange oil extract - eliminates any fishy taste or gas that is common with lower quality fish oil. Great news if you don't like fish!

**Full Transparency:** There's a difference between a fish oil supplement and an omega-3 supplement – we pride ourselves on being the later. We control the entire process from fish to final product to guarantee you the highest quality omega-3 supplement available.

**Sustainable:** Our products are accredited by Friend of The Sea (FOS) to ensure the highest standards in protecting the environment and fish populations.

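### The only adherence question with a unit counts days under a twice-daily regimen, and completers get no pill count, so the percentage of capsules taken cannot be reliably derived for them

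*Combined protocol and SAP*

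**What the plan says.** Section 6.1 sets the regimen at "3 mini-capsules, 2x/day (a total of 6 mini-capsules per day"; the placebo follows the same schedule. On duration, section 9.0 states "Each subject will spend 12 weeks in the study". Section 4.1 names the Appendix D follow-up survey as the instrument for feasibility and acceptability, the primary endpoint.

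That survey asks about intake in four places:

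- whether any dose was skipped during the study (No/Yes), with a prompt to consult the pill log calendar;
- if Yes, how often, with no unit or response categories shown;
- "For how many days in a typical week did you take the pills";
- a comment field on missed doses.

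The capsule count, "How many pills altogether do you have in your bottle(s) of supplement/placebo", is item 2 of the separate Study Discontinuation Verification form in Appendix D. Section 6.2 assigns that form to subjects who discontinue, whether removed for non-compliance or by their own choice. Item 3 of the form tells them to discard what is left.

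Section 14.0 (and 6.2) sets the compliance rule: "Any subject missing both daily doses 3 times a week for 3 weeks in a row will be removed from the study".

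Section 17.1 defines no adherence variable, unit or threshold. No section says that the pill log calendar is returned or entered as data.

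**The concern.** The one question that yields a usable number has a coarser unit than the regimen. A subject can be fully compliant by days and half compliant by doses, and the answer would be the same. The question that does refer to doses is binary, so one missed dose and 84 missed doses both read Yes, and its follow-up leaves each subject to choose a unit. The one instrument that measures capsules directly is withheld from the subjects who finish.

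Section 2.0 presents the study as proof of concept for a larger efficacy trial. Whether people will take six capsules in two daily doses for 12 weeks is among the first things the planners of that trial will want to know, as a percentage of the prescribed amount. The forms as drafted do not reliably provide it for completers.

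**Working it through.** **Inputs**

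- 2 doses a day, 3 capsules a dose (section 6.1).
- 12 weeks = 84 days (section 9.0).
- Day question on a 0 to 7 scale (Appendix D follow-up survey).
- Removal rule based on days with both doses missed (sections 6.2 and 14.0).

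**The plan's own figure first.** Section 6.1 states "Dose is 2,100mg per day via 3 mini-capsules, 2x/day (a total of 6 mini-capsules per day".

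- Appendix E says each mini-capsule "contains 350 mg of omega-3's": 6 × 350 = 2,100 mg, which reproduces the stated dose.
- Section 6.1 also says "Each capsule has 252mg of EPA and 102mg of DHA": 6 × (252 + 102) = 6 × 354 = 2,124 mg, which is 1.1% higher.

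The two content statements should be reconciled. The difference does not affect what follows, which is in doses and capsules.

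**Totals**

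- Doses: 84 × 2 = 168.
- Capsules: 168 × 3 = 504.

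**A completer who takes one of the two doses every day**

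- Doses taken: 84/168 = 50%. Capsules: 252/504 = 50%.
- Answer to the day question: 7 of 7.
- Answer in doses per week: 7 of 14 = 50%.
- Answer to the skipped-dose question: Yes.

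**What a given day answer is compatible with.** If d days are reported and at least one full dose is taken on each, dose adherence lies between d/14 and 2d/14.

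| Days reported | Lowest | Highest |
|---|---|---|
| 7 | 7/14 = 50% | 14/14 = 100% |
| 6 | 6/14 = 43% | 12/14 = 86% |
| 5 | 5/14 = 36% | 10/14 = 71% |

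The ranges overlap. A subject reporting 5 days with both doses (71%) has taken more than one reporting 7 days with one dose (50%).

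**A case that the dose question also misses.** A subject who takes 1 + 2 capsules a day where 3 + 3 are due has skipped no dose and could answer No. The day answer is 7, and capsules taken are 3 × 84 = 252 of 504 (50%).

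**A case where the day question is right.** Missing two whole days every week gives 5/7 = 71.4%. In doses, 168 − (2 × 2 × 12) = 120, and 120/168 = 71.4%. The error arises only when days are partly dosed.

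**The removal rule, taken separately.** It is an operational rule and not an adherence measure, but it also disregards single missed doses.

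- Both doses missed on 3 days a week for 3 weeks: 3 × 2 × 3 = 18 missed, 18/168 = 10.7%; the rule is met.
- One dose missed every day: 84/168 = 50%; the rule is never met.

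**The case against.** The strongest reply is that the day question does not stand alone. The question before it refers to skipped doses and points to the pill log; a subject who drops every evening dose must truthfully answer Yes, is then asked how often, and has a comment field. A free-text answer such as 'every evening' would reveal half-dosing. This stands, and it limits the point: the information can be captured, but not in a unit that can be relied on across subjects. It does not help with reduced capsules per intake.

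A second reply is that other safeguards exist. Omega-3 blood spots are taken at baseline and week 12 in both arms, and the coordinator calls every subject weekly, with any call notes kept in REDCap (section 17.3). These are real but partial. The blood spot is an indirect check in the omega-3 arm and cannot show missed soybean-oil placebo. No dose count is specified for the calls, and the bi-weekly survey in Appendix C has no intake question.

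Three stronger readings are tempting, and the documents support none of them:

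- *That adherence is scored in days, so half-dosing will be reported as full adherence, with a known upward bias.* No score is defined anywhere, and an analyst need not use the day question in isolation.
- *That a null symptom result could not be told apart from under-dosing.* The change in omega-3 level in the active arm bears directly on that, and section 17.1 says the study is not powered for its analyses in any case.
- *That completers and discontinuers are measured on different scales.* The Study Summary places the follow-up survey at the end of participation without restricting it to completers, so the discontinuation count may be an addition and not a replacement.

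**Conclusion.** The point holds as a measurement gap in the named source of the primary feasibility endpoint. For completers, the percentage of prescribed capsules taken cannot be reliably derived: the only question with a unit leaves a 7-day answer spanning 84 to 168 of 168 doses, the dose-level frequency question has no unit, and no capsule count is planned.

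The 50% lower limit assumes at least one full dose on each reported day; with part-doses it could be lower. The total of 504 assumes that all 84 days are due when the count is made. How many subjects would take partial daily doses is not known from the documents, so the size of any error in a reported average cannot be stated. The gap does not invalidate the study, but it is worth closing because closing it costs very little.

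**What to change.** 1. Add the existing remaining-pill question (item 2 of the Study Discontinuation Verification form) to the week-12 survey for every subject, placed before any instruction to discard.
2. Have the coordinator record the number of capsules shipped to each subject; the documents do not state it.
3. State in section 17.1 that adherence is (capsules shipped − capsules remaining)/504 for completers, and the same numerator over capsules due for those who stop early.
4. Reword the day question to ask for doses taken out of 14 in a typical week.
5. Collect the existing pill log calendar as a cross-check on the count.
6. Reconcile the removal wording in sections 6.2 and 14.0, which counts only days with both doses missed, with the dose-level measure. No removal rule is proposed here.

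The cost is one existing question copied, one reworded, one shipping figure recorded and one log returned; no visit, test or design change is needed. The downsides are that a self-reported count can overstate intake if capsules are discarded, and that the adherence reported may turn out lower than a count of days would suggest.

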## Study Discontinuation Verification

Please complete the survey.

Thank you!

- 1) Have you discontinued study participation?  Yes  No
- 2) How many pills altogether do you have in your bottle(s) of supplement/placebo? \_\_\_\_\_
- 3) Please discard all of the study supplement/placebo pills that you have, and indicate that here. Have you discarded your study supplement/placebo?  Yes  No

## Appendix E: Omega-3 Supplement & Labeling Information

 KD Nutra™ a KD Pharma Group Company [name] www.kdnutra.com	CERTIFICATE OF ANALYSIS																																																																	
Product Number: MSU1286 Product Description: Oceanblue® MiniCap® Placebo Formula Customer: Oceanblue LLC. Customer Item No.: N/A	Batch No: 2011090 Manufactured Date: November 24, 2020 Test Date:																																																																	

  
 Tests	Acceptance Criteria	Method	Results	
   
 Description	Clear transparent oval soft capsule containing pale yellow oil	STM001	Complies	
 
 Fill Weight	458 mg ±5%	USP <2091>	452 mg	
 
 Weight Variation	Meets USP <2091>	USP <2091>	Complies	
 
 Average Total Weight	647 mg ±10%	USP <2091>	645 mg	
 
 Rupture Test	Max. 15 Minutes	USP <2040>	1 minute	
 
 Total Aerobic Bacterial Count	<1,000 cfu/g	USP or equivalent	<1,000 cfu/g	
 
 Total Mold/Yeast Count	<100 cfu/g	USP or equivalent	<100 cfu/g	
 
 Enterobacteriaceae	<100 cfu/g	USP or equivalent	<100 cfu/g	
 
 Escherichia coli	Negative/10 g	USP or equivalent	Negative/10 g	
 
 Salmonella spp.	Negative/10 g	USP or equivalent	Negative/10 g	
 
 Staphylococcus aureus	Negative/10 g	USP or equivalent	Negative/10 g	
 
            Tooling Size: 7.5 Oval            Ingredients: Soybean Oil; Gelatin, Bovine; Glycerin; Purified Water; D-Limonene; Ethyl Vanillin.            Allergens: None*         	
 
            *Contains highly refined soybean oil. Labeling exempt per US Food Allergen Labeling and Consumer Protection Act (FALCPA)         	
 
            Approvals:            Quality Control: W.W. 	           Date: 12-09-20 	
 
            Quality Assurance: J.R.B. 	           Date: 12/10/20 	
  
			Tests	Acceptance Criteria	Method	Results	Description	Clear transparent oval soft capsule containing pale yellow oil	STM001	Complies	Fill Weight	458 mg ±5%	USP <2091>	452 mg	Weight Variation	Meets USP <2091>	USP <2091>	Complies	Average Total Weight	647 mg ±10%	USP <2091>	645 mg	Rupture Test	Max. 15 Minutes	USP <2040>	1 minute	Total Aerobic Bacterial Count	<1,000 cfu/g	USP or equivalent	<1,000 cfu/g	Total Mold/Yeast Count	<100 cfu/g	USP or equivalent	<100 cfu/g	Enterobacteriaceae	<100 cfu/g	USP or equivalent	<100 cfu/g	Escherichia coli	Negative/10 g	USP or equivalent	Negative/10 g	Salmonella spp.	Negative/10 g	USP or equivalent	Negative/10 g	Staphylococcus aureus	Negative/10 g	USP or equivalent	Negative/10 g	Tooling Size: 7.5 Oval Ingredients: Soybean Oil; Gelatin, Bovine; Glycerin; Purified Water; D-Limonene; Ethyl Vanillin. Allergens: None*				*Contains highly refined soybean oil. Labeling exempt per US Food Allergen Labeling and Consumer Protection Act (FALCPA)				Approvals: Quality Control: W.W.		Date: 12-09-20		Quality Assurance: J.R.B.		Date: 12/10/20	
Tests	Acceptance Criteria	Method	Results																																																															
Description	Clear transparent oval soft capsule containing pale yellow oil	STM001	Complies																																																															
Fill Weight	458 mg ±5%	USP <2091>	452 mg																																																															
Weight Variation	Meets USP <2091>	USP <2091>	Complies																																																															
Average Total Weight	647 mg ±10%	USP <2091>	645 mg																																																															
Rupture Test	Max. 15 Minutes	USP <2040>	1 minute																																																															
Total Aerobic Bacterial Count	<1,000 cfu/g	USP or equivalent	<1,000 cfu/g																																																															
Total Mold/Yeast Count	<100 cfu/g	USP or equivalent	<100 cfu/g																																																															
Enterobacteriaceae	<100 cfu/g	USP or equivalent	<100 cfu/g																																																															
Escherichia coli	Negative/10 g	USP or equivalent	Negative/10 g																																																															
Salmonella spp.	Negative/10 g	USP or equivalent	Negative/10 g																																																															
Staphylococcus aureus	Negative/10 g	USP or equivalent	Negative/10 g																																																															
Tooling Size: 7.5 Oval Ingredients: Soybean Oil; Gelatin, Bovine; Glycerin; Purified Water; D-Limonene; Ethyl Vanillin. Allergens: None*																																																																		
*Contains highly refined soybean oil. Labeling exempt per US Food Allergen Labeling and Consumer Protection Act (FALCPA)																																																																		
Approvals: Quality Control: W.W.		Date: 12-09-20																																																																
Quality Assurance: J.R.B.		Date: 12/10/20																																																																

Labeling: There will be only ONE label for both the placebo and IP, to keep the blind.

Investigational drug / Placebo label (below is the minimum that will be included)

- Subject ID#
- Expiration date (as per sponsor)
  - prescription (serial) number.
  - date of each dispensing.
  - subject's name.
  - directions for use.
  - name and strength of the drug product (or active ingredient(s) in a compounded prescription) -----> inv. IP name / Placebo
  - prescriber's name.
  - Initials of dispensing pharmacist.

Keep at Room Temperature between 59-86 °F

Caution: New Drug Limited by Federal (or U.S.) law to Investigational Use.

ega - Internet Explorer

ega.com/products/omega-3-minicaps    OMEGA-3 MINICAPS – Ocea... 

 **Product Details**

 **Supplement Facts**

 **Reviews**

**OMEGA-3 MINICAPS** deliver 700 mg of our high-purity pure omega-3 fatty acids in two easy-to-swallow mini-softgels. **OMEGA-3 MINICAPS** are the perfect way complement your wellness program and ensure you and your family are getting enough omega-3 fatty acids in your diet. **OMEGA-3 MINICAPS** are the highest concentration omega-3 fish oil available in pharmacies. They come in a great-tasting vanilla flavor. Each **MINICAP** contains 350 mg of omega-3's, which is three and a half times as strong as standard krill oil products.

**Supports Heart Health and Blood Circulation:** Supportive but not conclusive research shows that consumption of EPA and DHA omega-3 fatty acids with healthy diet and exercise may reduce the risk of coronary heart disease.

**A "Clean" Natural Source:** All our omega-3s come from wild-caught anchovies and sardines with zero to low mercury exposure off the coast of Peru.

**No Fishy-ness:** The purity of our oil - plus a natural orange oil extract - eliminates any fishy taste or gas that is common with lower quality fish oil. Great news if you don't like fish!

**Full Transparency:** There's a difference between a fish oil supplement and an omega-3 supplement – we pride ourselves on being the later. We control the entire process from fish to final product to guarantee you the highest quality omega-3 supplement available.

**Sustainable:** Our products are accredited by Friend of The Sea (FOS) to ensure the highest standards in protecting the environment and fish populations.

**oceanblue®**

[figure not shown]
SHOP ALL      

WHERE TO BUY  

CONTACT 

A screenshot of a computer screen displaying a webpage from Oceanblue. The page features a large, scenic image of snow-capped mountains and a calm lake. Overlaid on the left side is a large, stylized blue 'O' shape. The main title 'THE OCEANBLUE DIFFERENCE' is prominently displayed in white, bold, sans-serif capital letters. Below the title, the page is divided into three main sections: 'PURITY', 'POTENCY', and '3T'S OF OCEANBLUE'. Each section contains descriptive text and a call-to-action link.

PURITY	POTENCY	3T'S OF OCEANBLUE
More benefits. Less fat.  At Oceanblue, we create omega-3 supplements ... not run-of-the-mill fish oil supplements. What's the difference?  First our omega-3 oils are refined in Norway and then further concentrated in our state-of-the-art facility in Germany.  During this process, we remove unhealthy fats, impurities and by-products to create high-purity, concentrated omega-3 products.  Click here to learn more about why purity and concentration matters when choosing an omega-3 supplement.	What you need in fewer softgels.  When choosing an omega-3 supplement there are two important things to consider: 

▪ What is the amount of omega3s in a serving?

▪ How many softgels make up a serving?

 Depending on goals, you may need 500 mg to over 1,000 mg of omega-3s per day to see health benefits.  Being able to reach that daily dose in as few softgels as possible is critical to remaining committed to a supplement program.  Click here to learn more about why potency of omega-3s per serving is so important.	Transparency, Traceability, and Technology.  At Oceanblue, we control the entire process of creating our products from fish to final packaging. This allows us to provide transparency of all our ingredients and manufacturing processes as well as the ability to trace back our omega-3 oils to their source.  Since omega-3s are all that we do – and we do it well – you can trust our expertise to give you and your family the best products available.  Click here to learn more about how Oceanblue products get from our family to yours.

